After all Pre-testing is complete (including the NP tests), randomization and assignment for LED treatment to Group 1 (Sham 1st, Real 2nd), or to Group 2 (Real 1st, only) will take place. A total of 49 cases are treated per Group; approximately 98 total across the study. The PhD Study Coordinator will use the free computer software program GraphPad (graphpad.com), to assign the participants (10 at a time), using a blocked randomization procedure, into the 2 groups. After 10 participants have been assigned, another set of 10 participants will be randomized into Group 1 or 2 in the same manner. This method will continue to be used, until all cases have been treated, across the study period. The study coordinator at the Boston VA is responsible for assignment of randomization at the SF VA as well.

Participants are treated 2x per week (at least 48 hours between treatments), for 7.5 weeks in each series – total of 15 LED Tx.'s per LED series. **Blinding is preserved** because neither the participant, nor the Neuro-psychologist doing the Pre- Post- testing is aware of whether the patient has received Sham or Real LED.

"Transcranial, Light-Emitting Diode (LED) Therapy to Improve Cognition in GWVI" PI: [name].

Randomized, sham-controlled, study to examine effectiveness of transcranial LED in the near-infrared (NIR) wavelength to improve cognition (Attention, Executive Function, and Memory) in Veterans with Gulf War Veterans' Illness.

Control panel contains 5 switches. They may be used in any combination of On/Off positions.

- 1. On-off
- 2. Front only
- Left only
- 4. Right only
- 5. Midline only

Helmets are made up of 18 Omnilux New-U LED pods.

Omnilux New-U was FDA cleared in 2008 for reducing peri-orbital wrinkles and is sold over the counter.

Each LED pod: Power Output 665.3 mW Power density, 30.8 mW/cm² 20 NIR diodes, 830nm Emitter area: 21.6cm² 1 J/cm² = 32.5 sec 26 J/cm² = 14 min, 5 sec.

Each session, 2 stages: 1. Midline only, 14 m, 5 s 2. R and L sides together, 14 m, 5 s Total Treatment Time = 28 m, 10 s

Clear plastic liner, each case.

The LED Helmet manufactured by PhotoMedex, Montgomeryville, PA will be used (Fig. 19). This helmet contains 18 pods (LED cluster heads). Each pod is 4.5cm x 4.8cm. The helmet is designed with 6 pods to treat the midline of the head; 6 pods to treat the right side of the head; and 6 pods to treat the left side of the head.

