Dotted white lines on MRI in **a.** and **b.**, show expected direction of NIR (870 nm) photons, into bilateral frontal lobes (prefrontal cortex and anterior cingulate gyrus areas), with forehead placements. Additional placement sites are used, see text.

Each placement is applied simultaneously with the helmet during the last 4 min of Part 2 (Left and Right) and for

The chinstrap of the LED helmet will hold the LED cluster heads into place on the front of the L and R ear. All LED cluster heads are wiped with a disinfectant, after each treatment.

All appointments are scheduled ahead, for a specific day and time of day, (usually a Mon/Weds or a Tues/Thurs schedule). It is necessary to have at least 48 hours, between treatments.

If the participant needs to miss an appointment, that appointment will be re-scheduled so that all 15 LED treatments are completed, in each of the two LED treatment series. If a subject misses 2 weeks in a row without any treatment, the subject will be given the option to start over or be withdrawn from the study.

Statistical Analyses and Power Statement [name]; Statistician, VA IRB, Consultant on this project

Participants are likely to show different profiles for performance on individual tests on which they met entry criteria. Using all participants to examine efficacy test by test, will create a serious bias. Therefore, following the lead of the Neuropsychologists on our team ([name] and [name]) we will create 3 cognitive domain scores: Attention/Executive Functioning; Learning and Memory; and Psychomotor/Visual Spatial.

- 1) Attention/Executive Function: Digit Span Subtests (WAIS-IV; Wechsler, 2008); Trail-Making Test (Delis, Kaplan, Kramer, 2001); and Stroop Test ("Color-Word" test) (Delis, Kaplan, Kramer, 2001)
- 2) Learning and Memory: California Verbal Learning Test-II (CVLT-II; Delis, Kramer, Kaplan, & Ober, 2000)
- 3) Psychomotor/Visual Spatial; Continuous Performance Test (Administered on computer; RVisual CPT, NES3) (Letz & Baker, 1988; Rosvold et al., 1956); Rey Osterrieth Complex Figure Test (ROCF) (Knight & Kaplan, 2004)

Each of our individual tests has been standardized, and yields age/education/gender-adjusted z-scores. For each domain, we will compute the mean z-score from those tests that load for that factor (i.e., the two tests selected for Learning and Memory have a total of 9 standardized scores: the domain score will be the mean of these 9 values).

Analysis Plan:

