Preliminary Analyses: Before testing any of the stated hypotheses, the frequency distributions for all study variables will be examined, and appropriate transformations will be carried out whenever violations of normality are determined. Descriptive statistics and bivariate correlations will be computed. This will be necessary in order to test for colinearity among dependent variables. The number of variables will be constrained when r > .75. In addition, each variable will be tested for leptokurtosis to insure that there is a sufficient range of scores. Variables found to be significantly leptokurtic will be converted into dichotomous outcomes.

Tests of Hypotheses: All participants will be evaluated at Entry (Baseline) and within one week of completing either Sham Intervention or Real Intervention The main hypothesis will be tested by two-way mixed-design analysis of variance, with a trend analysis with treatment conditions as the between-groups variable and time of testing as the repeated-measures variable. To control for the fact that the dependent variables can co-vary and for the large number of F-tests to be computed, these analyses will be carried out by Multivariate Analysis of Variance (MANOVA) utilizing PASW v.18. Subsequent to the MANOVA, a series of univariate ANOVAs will be conducted for each dependent variable. Empirical effect sizes will be computed by partial eta². Headsize measurements will be used as covariates.

Power Analysis:

Primary Analysis: The primary analysis is between Real Only and Sham 1st. This comparison will be between groups. It is a parallel design for this primary analysis.

Power and sample size were computed for only the primary, between-group analysis using a moderate effect size appropriate to ANOVA.

The following computer software was used: Borenstein M, Rothstein H and Cohen J. Power and Precision (2004). Englewood, NJ, Biostat. We solved for sample size in order to obtain power = .80 given the following assumptions: alpha = .05 (1-tailed); power = .80; moderate effect size. ANOVA is always a 1-tailed test.

Cohen recommends that readers of his book who consider the ES range defined as 'Large" to be too small (or too large) to meet the appropriate standards of his/her area, should define alternative operational definitions (p.79). See table created below by the PIs from the content in Cohen (1988).

Statistic	ES Index	Small	Medium	Large
Correlation	r	.10	.30	.50

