Difference Between Correlations	q	.10	.30	.50
Proportion equal to .50	g	.05	.15	.25
Difference Between Proportions	ĥ	.20	.50	.80

Chi-Square	W	.10	.30	.50
F Test on Means (ANOVA/ANCOVA) *	f	.10	.25	.40
Multiple Regression	f ²	.02	.15	.35

* Please note, we used **f** as the ES Index for the power calculations submitted to the DMC.

Cohen, J. (1988). Statistical Power Analysis for the Behavioral Sciences (2nd Ed.). Lawrence Erlbaum Associates.

Secondary Analysis:

The Sham 1st shifted to Real will be a second test of efficacy of treatment, and subjects will be compared only within-subject.

In the secondary analyses the two groups will not be compared to one another.

Drop-Outs: In any longitudinal intervention study there will be participants who do not complete the protocol (missing data). The issue of missing data was addressed in a recent special report in the New England Journal of Medicine by an expert panel convened by the National Research Council (Little et al., 2012). Analyses utilizing only data from completers, even when intent-to-treat analyses have established no differences between these samples at Baseline, at best will yield an underestimation of standard errors and, at worst, can lead to biased results. They recommend using an acceptable multiple imputation (MI) procedure to "replace" missing values. Since the data are missing, in all likelihood, Not-At-Random (NAR), this will require generating a model accounting for missingness. Following the recommendations of Moon (Moon et al., 2006) we will utilize a flexible MI procedure known as MICE (multiple imputation by chained equations) on S⁺ and which will utilize the outcome for imputation of missing predictor values. Completers and non-Completers will be first compared on socio-demographic variables to predict the likelihood of completion by discriminant analysis. Any variables that discriminate Completers from non-Completers will be entered into our models as weighted covariates.

Interim Analyses: For both ethical and pragmatic reasons, we have a planned interim analysis at exactly the halfway point of the study, regardless of drop-out rate. To be conservative we will employ the O'Brien-Fleming alpha spending function to establish stopping boundaries. If the MANOVA is significant at p<.022, efficacy will be considered to be reliably established.

Tentative Sequence or Timetable

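### The primary mixed-design ANOVA/MANOVA treats Baseline as a level of time, which amounts to a change-score test; adjusting the one-week score for Baseline would be more precise at no data cost

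*Combined protocol and SAP*

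**What the plan says.** All references are to the combined protocol and SAP.

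- **Tests of Hypotheses** describes a two-way mixed-design ANOVA, run as a MANOVA and followed by univariate ANOVAs, with "treatment conditions as the between-groups variable and time of testing as the repeated-measures variable". On timing: "All participants will be evaluated at Entry (Baseline) and within one week of completing either Sham Intervention or Real Intervention". On covariates: "Headsize measurements will be used as covariates".
- **Power Analysis** gives the contrast: "The primary analysis is between Real Only and Sham 1st. This comparison will be between groups".
- **Drop-Outs** adds conditional covariates, screened from socio-demographic variables: "Any variables that discriminate Completers from non-Completers will be entered into our models as weighted covariates".
- **Statistical Analyses and Power Statement** defines the three outcomes: "For each domain, we will compute the mean z-score from those tests that load for that factor".
- **Section 2a. 3b** places the Baseline tests before allocation: "After all Pre-testing is complete (including the NP tests), randomization and assignment for LED treatment to Group 1" or Group 2 follows.
- **Interim Analyses** ties the halfway look to the same model: "If the MANOVA is significant at p<.022, efficacy will be considered to be reliably established".

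The plan nowhere enters the Baseline domain score as a covariate, and it gives no Baseline-to-one-week correlation.

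**The concern.** Treating Baseline as a second outcome measurement fixes its coefficient at 1: each person's Baseline is subtracted in full from the one-week score. When the regression of the one-week score on Baseline has a slope below 1, that over-corrects and adds noise. Entering Baseline as a covariate lets the data estimate the slope.

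Both tests are unbiased under randomization, so the issue is precision only. Precision matters here because the trial was sized for power .80 at a moderate effect, and section 2a. 3 says recruitment fell short of expectation. A pre-randomization covariate that is already collected is cheaper than more participants. The two covariate rules in the plan do not fill this role. Neither head size nor a socio-demographic predictor of drop-out is the Baseline score of the outcome itself.

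**Working it through.** **Inputs from the documents.** 49 per group, 98 in total (sections 2a. 3 and 2a. 3b); alpha .05; power .80; moderate effect, with medium f = .25 (Power Analysis table). For two equal groups d = 2f = 0.5.

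**Assumptions.** r = .5 to .8 (.9 also shown); two-sided .05, because an F test does not distinguish direction; between-domain correlation .5; the same effect in all three domains.

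**The plan's own figure.** A one-sided comparison at d = 0.5 needs 50 per group (normal approximation) or 51 (t test), and power at 49 per group is .797 or .792. The stated 49 is therefore reproduced as a one-sided calculation. An F test at alpha .05 with f = .25 has power .69 at N = 98. The rest of the check uses the F-test or two-sided basis.

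**Step 1: equivalence.** With two times, the group-by-time F equals the square of the t statistic on change scores. On simulated data both came to 12.359.

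**Step 2: error variance.** With equal SD at both times, in one-week SD units, the change score has variance 2(1 − r) and the adjusted score 1 − r². Their ratio is (1 + r)/2.

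| r | Change, 2(1 − r) | Adjusted, 1 − r² | Ratio | Reduction |
|---|---|---|---|---|
| .5 | 1.00 | .75 | .75 | 25% |
| .6 | .80 | .64 | .80 | 20% |
| .7 | .60 | .51 | .85 | 15% |
| .8 | .40 | .36 | .90 | 10% |
| .9 | .20 | .19 | .95 | 5% |

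Simulating 20,000 trials of 49 per arm gave ratios of .754 at r = .5 and .909 at r = .8.

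**Step 3: selection on low scores.** Suppose selection halves the Baseline variance and leaves the slope b unchanged (b takes the values of r above). The change variance is then 0.5(1 − b)² + 1 − b². At b = .5 this is .125 + .75 = .875, and .75/.875 = .857, a 14% reduction. For b = .6, .7 and .8 the reductions are 11%, 8% and 5%.

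**Step 4: power, equal variances.** Single domain: noncentral t with 96 df (change) or 95 df (adjusted). Three domains: noncentral F with 3 and 94 df (MANOVA) or 3 and 91 df (MANCOVA). With R the between-domain correlation matrix, d′R⁻¹d = 0.25 × 3/(1 + 2 × .5) = .375, and (49/2) × .375 = 9.1875.

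- In one-week SD units, divide 9.1875 by 2(1 − r) for the planned test, or by 1 − r² for the adjusted test.
- The adjusted value is also multiplied by 1 − 3/96, the cost of estimating three covariates.
- At r = .5 the noncentrality is 9.19 for the planned test (power .701) and 9.1875/.75 × .96875 = 11.87 for the adjusted test (power .818).
- In change-score SD units, the planned noncentrality is 9.1875 at every r, and the adjusted one is 9.1875 divided by (1 + r)/2, times 1 − 3/96.

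| r | One domain, one-week SD units | One domain, change SD units | Three domains, one-week SD units | Three domains, change SD units |
|---|---|---|---|---|
| .5 | .69 → .81 | .69 → .81 | .701 → .818 | .701 → .818 |
| .6 | .78 → .87 | .69 → .78 | .805 → .879 | .701 → .790 |
| .7 | .89 → .93 | .69 → .76 | .911 → .944 | .701 → .762 |
| .8 | .97 → .98 | .69 → .73 | .985 → .990 | .701 → .736 |

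At r = .9 in change units the three-domain gain is only .701 to .710.

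**Step 5: simulation.** With 6,000 trials per setting (three domains, correlation .5, change units), MANOVA power was .689/.702/.710/.700 and MANCOVA power .814/.792/.763/.733 for r = .5/.6/.7/.8. Over 3,000 null trials per r (correlation .3), type I error was .044 to .055 for MANOVA and .042 to .054 for MANCOVA.

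**The case against.** The planned test is valid, so this is a preference about efficiency, and the favourable figures rest on equal variances and a moderate r.

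- **Selection.** Entry requires low screening scores, and the screening CVLT-II and Stroop scores are carried over as Baseline. With halved Baseline variance, the three-domain gain in change units is only from .701 to .759/.742/.726/.711.
- **Larger one-week spread.** If the one-week SD were 1.25 times the Baseline SD (an assumption), the variance ratio would be .89/.94/.98/1.00 and MANCOVA power .740/.714/.695/.685. That is a small loss against .701 at r = .7 and .8.
- **Reading of the plan.** The group-by-time term is never named as decisive. The mention of a trend analysis leaves open whether the one-month test is also a time level, in which case the change-score equivalence fails.
- **Timing.** Participants learn their allocation after one-month testing. The halfway look may also be past: 50 Boston cases were projected for September 2017, half of 98 is 49, and the document is dated December 2017.

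What stands: the gain depends on r and on the variances, neither of which the documents give, and it can be close to nil. The loss arises only where the slope is near 1 (r × 1.25 = .875 and 1.00), so adjustment saves little or nothing and the covariate cost of about 3% remains. The sentence that sets the test times lists only two. If the one-month test were added, Baseline would still be an outcome level and not a covariate. The timing point bears on which remedy is open, and the fix allows for it.

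**Conclusion.** The concern holds. As written, the primary model uses Baseline as an outcome level, and with the two named times it tests change scores. Adjusting for Baseline lowers error variance by 25% to 10% for r = .5 to .8 with equal variances, or 14% to 5% if selection halves the Baseline variance. The gain is worthwhile at r of about .5 to .7 and small at .8 or above. Apart from the cost of estimating the covariates, the adjusted error variance never exceeds that of the change score. This is a missed gain in precision. It is not an error that biases the result, and the change should be made if the primary analysis can still be altered.

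**What to change.** Before unblinded data are analysed, amend the analysis plan as follows.

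1. Make the primary test the Real versus Sham effect in an ANCOVA/MANCOVA of the one-week domain scores, with the Baseline domain score(s) as covariate(s). Keep head size and the covariates from Drop-Outs.
2. Report the group-by-time result of the mixed-design ANOVA as supportive.
3. State that the interim boundary applies to the same adjusted model.
4. If the halfway look has already taken place, which the documents do not say, keep the planned MANOVA as primary and pre-specify the adjusted model as a sensitivity analysis.

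The cost is a change of wording, including the interim rule; no new data are needed. Each covariate uses about one degree of freedom: one for a single-domain ANCOVA and three for the MANCOVA. Estimating them inflates the variance of the treatment effect by about 1% and 3%. The three-domain adjusted powers above include this.
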